**CONFIDENTIAL**

Date:	16 July 2020	Novo Nordisk
Version:	5.0	
Status:	Final	
Page:	93 of 125	

values are assumed to respond as if treated with placebo for the entire trial. Multiple copies (N = 1000) of the full dataset will be generated by imputing missing values based on estimated parameters for the placebo group. This will be done as follows.

- In the first step, N = 1000 copies of the dataset will be generated.
- In the second step, an enriched ANCOVA model with sex, region, stratification factor for Tanner stage, baseline glycaemic category and interaction between baseline glycaemic category and stratification factor for Tanner stage as fixed effects and baseline BMI SDS, as covariate is fitted to the change from baseline in BMI SDS at 16 weeks (or 52 weeks) for the completers in the placebo group only.
- For each of the N copies of the dataset, the estimated parameters and their variances from this model are used to impute missing values at 16 weeks (or 52 weeks) for subjects in both treatment arms, based on their factor levels and the values of the covariates.
- For each of the N complete datasets, the change from baseline in BMI SDS at 16 weeks (or 52 weeks) is analysed using the main ANCOVA model with treatment, sex, region, baseline glycaemic category, stratification factor for Tanner stage and interaction between baseline glycaemic category and stratification factor for Tanner stage as fixed effects, and baseline BMI SDS and baseline age as covariates.
- The estimates and SDs for the N data sets are pooled to one estimate  $m_{MI}$  and associated  $SD_{MI}$  using Rubin's formula:

$$m_{MI} = \frac{1}{100} \sum_{i=1}^{100} m_i, \quad SD_{MI} = \sqrt{\frac{1}{100} \sum_{i=1}^{100} SD_i^2 + \left(1 + \frac{1}{100}\right) \left(\frac{1}{100 - 1}\right) \sum_{i=1}^{100} (m_i - m_{MI})^2},$$

where  $m_i$  and  $SD_i$  are the estimated means and standard deviations for the N copies of the dataset. From  $m_{MI}$  and  $SD_{MI}$ , the 95% CI for the treatment difference and the associated p-value are calculated.

If N = 1000 copies are insufficient to obtain stable results, a higher number will be used.

The MI method assumes that withdrawn subjects with missing values in the placebo arm have a response similar to the completers in the in the placebo arm given similar baseline characteristics. In the active arm the assumption is that withdrawn subjects with missing values behave as if they have been in the placebo arm during entire trial regardless of the time of withdrawal. In this way the assumptions are differential and conservative for estimating the treatment effect. The estimate in the primary analysis can be said to be an intention to treat (ITT) estimator or an effectiveness estimand of the add-on effect of liraglutide to dietary and physical activity counselling.

If the imputation ANCOVA model cannot be estimated due to too few placebo subjects with available data, explanatory variables will be removed in the following order until the model is

Protocol: Liraglutide  
Trial ID: NN8022-4179  
UTN: U1111-1162-7884  
EudraCT no.: 2014-004415-37

~~CONFIDENTIAL~~

Date: 16 July 2020  
Version: 5.0  
Status: Final  
Page: 94 of 125

**Novo Nordisk**

estimable: region, sex, baseline BMI SDS, Tanner stage, baseline glycaemic category and interaction between baseline glycaemic category and stratification factor for Tanner stage.

### Sensitivity analysis

To investigate the sensitivity of the results of the main analysis of the primary endpoint with regard to the handling of missing data, the following sensitivity analyses will be performed:

- An ANCOVA will be performed with imputation of missing values according to the last observation carried forward (LOCF) method. The model will include terms for treatment, sex, region, baseline glycaemic category, stratification factor for Tanner stage and interaction between baseline glycaemic category and stratification factor for Tanner stage, and baseline BMI SDS and baseline age as covariates. The response variable will be the last available measurement of BMI SDS obtained within the 16-week double-blind period of the trial. Data from nominal visits (V10x and V19x) will not be used for this analysis.
- The same type of ANCOVA as above will be performed, but using an imputation of missing values according to the baseline observation carried forward (BOCF) method. Missing measurements of BMI SDS at 16 weeks will with this method be imputed by the corresponding baseline values.
- The same type of ANCOVA as above will be performed without imputation by only including subjects who completed the 16-week double-blind period.
- A mixed model for repeated measurements (MMRM) will be applied where all post baseline BMI SDS measurements obtained at planned visits during the 16-week double-blind period will enter as the dependent variables, and visit, treatment, sex, region, baseline glycaemic category, stratification factor for Tanner stage and interaction between baseline glycaemic category and stratification factor for Tanner stage will be included as fixed effects, and baseline BMI SDS and baseline age as covariates. All these factors and covariates will be nested under visit, which is technically the same as introducing the corresponding interaction terms in the model. An unstructured covariance matrix for the BMI SDS measurements within subject will be employed.

The sensitivity analyses will be repeated for the week 52 co-primary endpoint.

The ANCOVA model with LOCF assumes that post treatment discontinuation, the body weight is on average stable in both treatment arms. If the assumption holds, the treatment effect (effectiveness estimand) in each arm and the treatment difference can be estimated from this analysis unbiased. If the withdrawal and the development in both arms are similar, the treatment difference can be estimated from this analysis unbiased. If the development in body weight after treatment discontinuation differs between active and placebo, this analysis might provide an optimistic or over-conservative estimate, depending on the actual circumstances. The analysis is included to be

Protocol: Liraglutide  
Trial ID: NN8022-4179  
UTN: U1111-1162-7884  
EudraCT no.: 2014-004415-37

~~CONFIDENTIAL~~

Date: 16 July 2020  
Version: 5.0  
Status: Final  
Page: 95 of 125

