### **8.1.8 Discontinuation of trial product**

See section [6.4](#) for discontinuation of trial product criteria. For subjects with discontinuation of trial product, the investigator must at a minimum aim to:

- undertake procedures for the end of treatment visit (V19) as soon as possible and
- schedule a follow up visit (V20) two weeks later.

Depending on when the discontinuation of trial product takes place during the trial:

- If trial product is discontinued between V3 and V9, the subject should attend V10x (16 weeks after V3) and V19x (52 weeks ( $\pm$  5 days) after V3)
- If trial product is discontinued between V11 and V19, the subject should attend V19x (52 weeks ( $\pm$  5 days) after V3)

The end-of-trial form must be completed, and final drug accountability must be performed. A treatment discontinuation session must be made in the IV/WRS. The case book must be signed.

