**17.2 Definition of analysis sets**

The following analysis sets are defined in accordance with the ICH-E9 guideline.

FAS: Includes all randomised subjects who have received at least one dose of trial product and have any post-randomisation data. The statistical evaluation of the FAS will follow the intention-to-treat (ITT) principle and subjects will contribute to the evaluation “as randomised”.

SAS: Includes all subjects exposed to at least one dose of trial product. Subjects in the SAS will contribute to the evaluation “as treated”.

Data from nominal visits (V10x and V19x) will be used prior to imputation of remaining missing data unless otherwise stated.

Before data are locked for statistical analysis, a blind review of all data will take place. Any decision to exclude a subject or single observations from the statistical analysis is the joint responsibility of the trial statistician, the ITM and the medical specialist. Exclusion of data from analyses will be used restrictively and normally no data should be excluded from the FAS. The subjects or observations to be excluded, and the reasons for their exclusion must be documented and signed by those responsible before database lock. The subjects and observations excluded from analysis sets, and the reason for this, will be described in the clinical trial report.

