**Novo Nordisk**

able to compare the results with legacy obesity programs, where this analysis was the main analysis of the primary endpoints.

The ANCOVA model with BOCF assumes that post treatment withdrawn subjects with missing values returns to a body weight in the proximity of their baseline body weight regardless of the timing of withdrawal. This analysis is expected to provide a conservative estimate (effectiveness estimand) of the treatment effect (in each arm). The impact of this assumption on the treatment difference depends on withdrawal pattern over time and development of body weight post withdrawal and reason for withdrawal. The analysis is typically expected to provide a conservative estimate of the treatment difference (effectiveness estimand).

The MMRM model assumes that withdrawn subjects, had they completed the trial, would not have behaved differently than completing subjects from the same treatment arm with the same baseline characteristics and change in body weight at time of withdrawal. This analysis estimates the treatment difference had all subjects stayed on the randomised treatment (efficacy estimand).

The ANCOVA analysis in completers is expected to give more positive results than the primary analysis. However, this analysis has its own clinical interpretation and will serve as a benchmark and provide an estimate of the efficacy estimand in the population that tolerate the trial product and endure the diet and exercise counselling program.

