**Table 5-2 Taxonomy for subjects based on of week 16 and 52 assessments being available or missing**

Assessment at week 16 and 52	On randomised treatment at week 16 and 52	Type description	Type abbreviation
Available	Yes	Available on randomised treatment: Subjects who did not discontinue randomised treatment prematurely with an assessment at week 16 and 52.	AT
	No	Available drop-outs: Subjects who discontinued randomised treatment prematurely but returned to have an assessment at week 16 and 52; also called retrieved drop-outs.	AD
Missing	Yes	Missing on randomised treatment: Subjects who did not discontinue randomised treatment prematurely without an assessment at week 16 and 52.	MT
	No	Missing drop-outs: Subjects who discontinued randomised treatment prematurely and did not return to have an assessment at week 16 and 52; also called non-retrieved drop-outs.	MD

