**Primary approach for handling missing values**

The primary approach for multiple imputations of missing values of BMI SDS at week 16 and 52 (type MT+MD [Table 5-2](#)) for both the liraglutide 3.0 mg and placebo group is by sampling all available assessments at respective landmark visits in the placebo group (type AT+AD). This approach is also known as jump to reference and makes the assumptions that subjects instantly after discontinuation lose any effect of randomised treatment beyond what can be expected from placebo treatment as adjunct to diet and exercise. The multiple imputation approach is done in four steps.

**Imputation:** Step 1: 1000 copies of the dataset will be generated.

**Analysis:** Step 2: Impute the missing value from placebo completers by fitting enriched regression model. Model will be fitted with the factors, covariates and interaction term in the same order as mentioned in [Table 5-3](#). The estimated parameters and their variances from this model were used to impute missing values at 16 weeks (or 52 weeks) for subjects in both treatment arms, based on their factor levels and the values of the covariates.

**Analysis:** Step 3: For each of the 1000 complete datasets, the change from baseline in BMI SDS at 16 weeks (or 52 weeks) will be analysed using the main ANCOVA model with factors and covariates and interaction term as mentioned in [Table 5-1](#).

**Pooling:** Step 4: Pool the 1000 estimation results into final result using Rubin's formula.

If N = 1000 copies are insufficient to obtain stable results, a higher number will be used.

The imputation model in step 2 uses placebo subjects from FAS with non-missing BMI SDS at baseline and 16 weeks (or 52 weeks). The imputation model is a linear regression of BMI SDS at 16 weeks (or 52 weeks) on the factors and covariates listed in [Table 5-3](#) (except randomised treatment arm) with interaction term included in the model. The order of the factors and covariates has been retained as mentioned in [Table 5-3](#) while fitting imputation model. The estimated posterior distribution for the parameters (regression coefficients and variances) in the imputation model is then used to impute missing 16 weeks (or 52 weeks) BMI SDS values for both randomised treatment arms.

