### 6.2.1 Primary endpoints

- Due to the COVID-19 pandemic, the primary endpoint assessments (body weight and height) for very few subjects in part B could not be performed at the end of the double-blind period of the trial – Visit 10 (Week 16) or at the end of the open-label period of the trial – Visit 19 (Week 52). These measurements (missing or performed at home) will not be part of the primary analysis. An additional analysis will be performed by including the subjects impacted by COVID-19 at week16 and 52 for the change from baseline in BMI SDS.
- For the sensitivity analysis using LOCF method the protocol mentions that data from nominal visits (V10x and V19x) will not be used .Similarly for sensitivity analysis using BOCF, MMRM and week 16/52 completer analysis, data from nominal visits (10x and 19x) will be excluded.

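### Under the SAP, every missing-data sensitivity analysis of the co-primary endpoints drops observed V10x/V19x values that the main analysis uses, so none isolates the jump-to-reference assumption

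*Protocol*

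**What the plan says.** Protocol 17.2 sets the default: "Data from nominal visits (V10x and V19x) will be used prior to imputation of remaining missing data unless otherwise stated". SAP section 4 repeats it.

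These visits come from subjects who stop trial product. Protocol 8.1.8 states: "If trial product is discontinued between V3 and V9, the subject should attend V10x (16 weeks after V3"), and V19x at week 52. The flow chart schedules weight and height at both visits, so BMI SDS is available there.

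SAP Table 5-2 classes such subjects as available (type AD): "Subjects who discontinued randomised treatment prematurely but returned to have an assessment at week 16 and 52; also called retrieved drop-outs". Only types MT and MD, on and off treatment with no landmark assessment, are imputed. The imputation works by "sampling all available assessments at respective landmark visits in the placebo group (type AT+AD"), which the SAP calls jump to reference.

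The purpose of the sensitivity analyses, in protocol 17.3, is "To investigate the sensitivity of the results of the main analysis of the primary endpoint with regard to the handling of missing data". In that section the exclusion, "Data from nominal visits (V10x and V19x) will not be used for this analysis", appears in the LOCF bullet only. SAP 5.3.3 repeats it under all four analyses, and SAP 6.2.1 records the extension as a change to the protocol: "Similarly for sensitivity analysis using BOCF, MMRM and week 16/52 completer analysis, data from nominal visits (10x and 19x) will be excluded". It gives no reason beyond the analogy with LOCF.

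On targets, protocol 17.3 and SAP 5.3.3 assign MMRM and completer ANCOVA to an efficacy estimand, and LOCF and BOCF to an effectiveness estimand. Protocol 17.3 uses the effectiveness label for the main analysis too.

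**The concern.** A missing-data sensitivity analysis should hold the observed data fixed and change only what is assumed about values nobody measured. Under the SAP, all four also change the observed data. If one of them departs from the main result, the gap may reflect the deleted off-drug values, the different assumption for MT and MD subjects, or both. Agreement is equally hard to read, because the two changes can offset each other.

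BOCF shows the conflict most plainly. Protocol 17.3 describes it for subjects who have no value: "The ANCOVA model with BOCF assumes that post treatment withdrawn subjects with missing values returns to a body weight" close to baseline. With V10x/V19x excluded, a subject measured at week 16 or 52 is treated as missing, and the measured value is replaced by baseline. LOCF likewise sets aside the measured landmark value in favour of an earlier one. Both keep the main analysis's effectiveness label.

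At stake is whether the robustness statement for the two co-primary endpoints can be interpreted.

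**Working it through.** **1. The plan's own figure.** Inputs from protocol 17.1: difference -0.23, SD 0.25, withdrawal 10%, 2:1 allocation, 80% power, two-sided 5%.
- Corrected difference: 0.9 x 0.23 = 0.207.
- Corrected SD: sqrt(0.25^2 + (2/3)(0.1)(0.9)(0.23^2)) = 0.2563.
- With 38 v 19 subjects, noncentral-t power is 0.806. The smallest 2:1 total reaching 80% is 57, as stated.

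The same method reproduces every cell of Table 17-1.

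**2. What each analysis does with each type of subject.**

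| Analysis | Off drug, landmark value observed (AD) | No landmark value (MT, MD) | Declared target |
|---|---|---|---|
| Main | observed value used | imputed from placebo | effectiveness |
| LOCF | earlier value used instead | last value | effectiveness |
| BOCF | replaced by baseline | baseline | effectiveness |
| Completer ANCOVA | left out | left out | efficacy |
| MMRM | V10x/V19x value ignored | modelled from own arm | efficacy |

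No row keeps the main analysis's second column and changes only the third. The additional COVID-19 analysis (SAP 5.3.2.2, 6.2.1) changes which part B measurements contribute, not the jump-to-reference assumption.

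**3. Illustration with nothing missing.** Assumptions: every discontinuer attends the x visit; a fraction q discontinues in each arm; placebo change is 0; on-drug effect D = -0.23; a fraction r = 0.5 of D is present at the last on-drug value; a fraction f of D remains at the x visit. Expected differences:
- Main = (1-q)D + qfD
- LOCF = (1-q)D + qrD
- BOCF = (1-q)D
- Completers = D

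| q | f | Main | LOCF | BOCF | Completers |
|---|---|---|---|---|---|
| 0% | any | -0.230 | -0.230 | -0.230 | -0.230 |
| 10% | 0 | -0.207 | -0.219 | -0.207 | -0.230 |
| 20% | 0 | -0.184 | -0.207 | -0.184 | -0.230 |
| 20% | 0.5 | -0.207 | -0.207 | -0.184 | -0.230 |

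At q = 20%, f = 0, the gaps from main are 0.023 (LOCF) and 0.046 (completers). The standard error of the difference is about 0.25 x sqrt(1/38 + 1/19) = 0.070, so these are about one third and two thirds of a standard error.

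BOCF matches main only when the assumptions line up. With 20% discontinuing on liraglutide, 10% on placebo, placebo drift +0.1 and f = 0, BOCF is 0.8(0.1 - 0.23) - 0.9(0.1) = -0.194, against main at -0.184.

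**4. Single data sets.** In 20,000 simulated trials (38 v 19, f = 0, placebo change 0), LOCF, BOCF and completers each differed from main in 99.8% of trials at q = 10% and in all at q = 20%. The first figure is simply the chance of at least one discontinuer among 57: 1 - 0.9^57 = 0.998. Mean absolute gaps for LOCF, BOCF and completers were 0.017, 0.017 and 0.028 at 10%, and 0.028, 0.025 and 0.050 at 20%. MMRM was not fitted.

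**5. With V10x/V19x values kept.** If nothing is missing, nothing is imputed. LOCF, BOCF and ANCOVA on observed values then equal the main estimate exactly, as a missing-data sensitivity analysis should.

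**The case against.** The strongest reply is that much of this is disclosed and fits the stated targets.
- MMRM and completer ANCOVA are declared efficacy analyses, for which leaving out off-drug values is coherent. Completer ANCOVA excludes those who stop by definition, and the plan warns that it should look more favourable. This stands; neither analysis is defective.
- LOCF is said to be there for comparison with earlier obesity programmes and possibly biased in either direction. This stands as to purpose, but does not justify the effectiveness label once observed off-drug values are ignored.
- The 17.2 default allows exceptions, and the SAP records its exclusions as changes. This stands procedurally, but does not reconcile the BOCF rule with its description.

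Several stronger readings are tempting and are not supported:
- A reader might infer that the protocol itself excludes V10x/V19x from all four analyses. Its text does so for LOCF only; the rest comes from the SAP.
- A reader might infer that jump to reference goes untested. LOCF, BOCF and MMRM do replace it for MT and MD subjects. The test is confounded, not absent.
- A reader might infer that results must differ even with complete data. That needs at least one discontinuer with an observed landmark value; with none, there is nothing to discard.
- A reader might infer that only the liraglutide arm is affected at week 52. Placebo subjects who stop between V3 and V9 are also sent to V10x and V19x.
- A reader might infer gaps of 0.05 to 0.09 SDS (27-50% of the main estimate). Those need every stopper retrieved, and the full effect present at the last on-drug value and wholly lost by the x visit. The upper end also needs a 0.5 correlation between poor response and stopping. It reflects completer selection, which the V10x/V19x rule does not cause.

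**Conclusion.** The point holds in this form. Given at least one retrieved drop-out, every sensitivity analysis listed in SAP Table 5-4 mixes deletion of observed off-treatment values with a change of assumption, and none isolates jump to reference for MT and MD subjects. The defect that the plan does not declare lies in LOCF and BOCF.

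The size is modest and depends on assumptions. In the illustration LOCF moves 0.012 SDS at 10% discontinuation and 0.023 at 20%, and not at all if half the effect persists at the x visit. BOCF can agree with main on average. The documents give no retrieval rate, so the actual gap cannot be predicted.

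Superiority is decided on the main analysis. The sample size, the 5% level and the primary test are untouched. What suffers is the interpretation of the robustness check, which should be put right.

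**What to change.** 1. In SAP 5.3.3 and 6.2.1, restore the protocol 17.2 default for BOCF: use observed V10x/V19x values and impute baseline only for MT and MD subjects.
2. Add a rerun of the main MI ANCOVA on the same data, V10x/V19x included, changing only the imputation of MT and MD subjects. Either missing at random within arm, or a delta shift increased until significance is lost, would serve. Do this for weeks 16 and 52.
3. Keep LOCF, completer ANCOVA and MMRM without V10x/V19x, labelled as supplementary on-treatment or legacy analyses, and remove the effectiveness label from LOCF.

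The cost is a few SAP lines and two extra model runs on data already collected. The added results may look less favourable than LOCF or completers.

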**Novo Nordisk**

able to compare the results with legacy obesity programs, where this analysis was the main analysis of the primary endpoints.

The ANCOVA model with BOCF assumes that post treatment withdrawn subjects with missing values returns to a body weight in the proximity of their baseline body weight regardless of the timing of withdrawal. This analysis is expected to provide a conservative estimate (effectiveness estimand) of the treatment effect (in each arm). The impact of this assumption on the treatment difference depends on withdrawal pattern over time and development of body weight post withdrawal and reason for withdrawal. The analysis is typically expected to provide a conservative estimate of the treatment difference (effectiveness estimand).

The MMRM model assumes that withdrawn subjects, had they completed the trial, would not have behaved differently than completing subjects from the same treatment arm with the same baseline characteristics and change in body weight at time of withdrawal. This analysis estimates the treatment difference had all subjects stayed on the randomised treatment (efficacy estimand).

The ANCOVA analysis in completers is expected to give more positive results than the primary analysis. However, this analysis has its own clinical interpretation and will serve as a benchmark and provide an estimate of the efficacy estimand in the population that tolerate the trial product and endure the diet and exercise counselling program.

